5.2 DEFINITION OF DOSE-LIMITING TOXICITY

Dose-limiting toxicity (DLT) of the KRd regimens will be evaluated during Cycle 1 (Cohorts 1, 2, and 3), or Cycles 1 and 2 (Cohort 4), of the Dose-evaluation Component. Subjects in the Dose-evaluation Component of the study who do not complete the dose evaluation period for reasons unrelated to toxicity will be considered unevaluable for DLT and may be replaced. DLT are the toxicities defined below and attributable to carfilzomib, lenalidomide, or dexamethasone.

5.2.1 *NONHEMATOLOGIC DLT*

- \geq Grade 3 nonhematological toxicity (excluding nausea, vomiting, diarrhea, alopecia, fatigue lasting < 14 days, increased serum creatinine or electrolyte abnormalities that are not clinically significant and require no treatment)
- \geq Grade 3 acute kidney injury (creatinine $> 3 \times$ baseline or > 4.0 mg/dL) lasting > 72 hours
- \geq Grade 3 nausea, vomiting, or diarrhea uncontrolled by maximal antiemetic/antidiarrheal therapy

5.2.2 *HEMATOLOGIC DLT*

- Grade 4 neutropenia (absolute neutrophil count [ANC] $< 500/\text{mm}^3$) lasting for > 7 days
- Febrile neutropenia (ANC $< 1000/\text{mm}^3$ with a fever $\geq 38.3^\circ\text{C}$) of any duration
- Grade 4 thrombocytopenia (platelet count $< 25,000/\text{mm}^3$) that persists for > 14 days with or without platelet transfusion, despite holding treatment
- Grade 3 or 4 thrombocytopenia (platelet count $< 50,000/\text{mm}^3$) associated with $>$ Grade 1 bleeding

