5 STUDY DESIGN

This is an open-label, multicenter, Phase 1b, dose-finding study of carfilzomib administered once-weekly in combination with lenalidomide and dexamethasone (KRd) in 28-day cycles to subjects with multiple myeloma.

Subjects may continue to receive study treatment for up to 18 cycles or until 1 or more of the following events occurs:

- Disease progression
- Allogeneic stem cell transplant
- Withdrawal from the study for any reason
- Study termination by the sponsor
- Death

Disease assessments will be conducted at Screening (within 21 days before dosing on Cycle 1 Day 1) and then on Day 1, \pm 3 days, of every cycle beginning with Cycle 2.

Response will be evaluated using the International Myeloma Working Group (IMWG) - Uniform Response Criteria (URC; [Rajkumar, 2011](#); [Appendix C](#)).

NDMM subjects may interrupt study treatment to proceed to hematopoietic stem cell collection, or stem cell collection and ASCT. The investigator will communicate transplant plans with the clinical study team. Upon completion of collection, subjects may resume study treatment (for up to the total of 18 cycles). Study treatment interruption for autologous hematopoietic stem cell collection may not exceed 42 days. Subjects with interruptions longer than 42 days may resume therapy on trial only with the written permission of the

sponsor study medical monitor. Subjects may interrupt study treatment and proceed to ASCT at any time after Cycle 4. Subjects who undergo ASCT may resume study treatment at any time up to posttransplant day 100, as elected by the investigator.

There will be 2 parts in the study.

The first part is the Dose-evaluation Component during which carfilzomib combination regimens will be evaluated ([Table 2](#) and [Figure 1](#)). Approximately 8 dose-limiting toxicity evaluable subjects will be enrolled into each opened Dose-evaluation cohort. Before opening Dose-expansion **arms**, it must be determined that there are not more than 2 dose-limiting toxicities in 8 DLT-evaluable subjects at the dose selected for Dose-expansion.

Dose-expansion **arms** may open once all safety data for at least 1 cycle at maximal dose carfilzomib is reviewed by the CSRC.

[figure not shown]
The second part is the Dose-expansion Component.

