9.2.2.1 Hematologic Toxicity

Guidelines for dose modification in the event of thrombocytopenia are summarized in [Table 7](#) and those for neutropenia in [Table 8](#).

Table 7 Treatment Guidelines for Thrombocytopenia

When Platelets:	Recommended Action					
	Lenalidomide	Carfilzomib				
Fall to $< 30 \times 10^9/L^a$	
• Hold dose, follow CBC weekly• Hold prophylactic anticoagulation until platelets return to $\geq 30 \times 10^9/L^a$• Then resume at 1 dose decrement	

If platelets $10-30 \times 10^9/L$ without evidence of bleeding	
• Hold• With resolution restart at previous dose	

If evidence of bleeding or platelets $< 10 \times 10^9/L$	
• Hold• With resolution restart at 1 dose decrement	

	If platelets $10-30 \times 10^9/L$ without evidence of bleeding	
• Hold• With resolution restart at previous dose	If evidence of bleeding or platelets $< 10 \times 10^9/L$	
• Hold• With resolution restart at 1 dose decrement
If platelets $10-30 \times 10^9/L$ without evidence of bleeding	
• Hold• With resolution restart at previous dose					
If evidence of bleeding or platelets $< 10 \times 10^9/L$	
• Hold• With resolution restart at 1 dose decrement					
For each subsequent drop to $< 30 \times 10^9/L^a$	
• Hold dose, follow CBC weekly• Hold prophylactic anticoagulation until platelets return to $\geq 30 \times 10^9/L^a$• Then resume at additional dose decrement	

If platelets $10-30 \times 10^9/L$ without evidence of bleeding	
• Hold• With resolution restart at previous dose	

If evidence of bleeding or platelets $< 10 \times 10^9/L$	
• Hold• With resolution restart at 1 dose decrement	

	If platelets $10-30 \times 10^9/L$ without evidence of bleeding	
• Hold• With resolution restart at previous dose	If evidence of bleeding or platelets $< 10 \times 10^9/L$	
• Hold• With resolution restart at 1 dose decrement

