If platelets $10-30 \times 10^9/L$ without evidence of bleeding	
• Hold• With resolution restart at previous dose					
If evidence of bleeding or platelets $< 10 \times 10^9/L$	
• Hold• With resolution restart at 1 dose decrement					

CBC = complete blood count.

^a For subjects entering the study with myeloma involvement in the bone marrow $> 50\%$, a lower threshold of $20 \times 10^9/L$ may be applied for lenalidomide dose reductions.

Table 8 Treatment Guidelines for Neutropenia

When ANC:	Recommended Action		
	Lenalidomide	Carfilzomib	
Falls to $< 0.75 \times 10^9/L$	
 Hold dose, administer myeloid growth factor Follow CBC weekly Resume at full dose when $ANC \geq 0.75 \times 10^9/L$ 	If $ANC 0.5-0.75 \times 10^9/L$	
 Continue at full dose
		If $ANC < 0.5 \times 10^9/L$	
 Hold dose Resume at 1 dose decrement when $ANC \geq 0.5 \times 10^9/L$
For each subsequent drop to $< 0.75 \times 10^9/L$	
 Hold dose, administer myeloid growth factor Follow CBC weekly Resume at 1 dose decrement when $ANC \geq 0.75 \times 10^9/L$ 	If $ANC 0.5-0.75 \times 10^9/L$	
 Continue at full dose
		If $ANC < 0.5 \times 10^9/L$	
 Hold dose Resume at 1 dose decrement when $ANC \geq 0.5 \times 10^9/L$

ANC = absolute neutrophil count; CBC = complete blood count.

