10.1.6 CLINICAL LABORATORY TESTS

Clinical laboratory assessments will include the following:

- Hematology: hemoglobin, hematocrit, white blood cell (WBC) with complete differential (total neutrophils, lymphocytes, monocytes, eosinophils, basophils), RBCs, platelet count
- Full serum chemistry panel: sodium, potassium, chloride, bicarbonate, blood urea nitrogen (BUN), creatinine, glucose, calcium, magnesium, phosphate, AST, ALT, total protein, albumin, alkaline phosphatase, total bilirubin, uric acid, and lactate dehydrogenase (LDH)
- Abbreviated chemistry panel: sodium, potassium, chloride, bicarbonate, BUN, creatinine, glucose
- Coagulation tests: prothrombin time, activated partial thromboplastin time, and international normalized ratio

Hematology and serum chemistry (full or abbreviated) will be performed at Screening, on Days 1, 8, and 15 of each cycle, and at EOT. On Days 8 and 15 of each cycle, from Cycle 2 onwards, an abbreviated serum chemistry panel may be performed. Coagulation will be performed at baseline and at EOT. For screening laboratory samples, historical panel may be used if within 21 days prior to dosing on Cycle 1 Day 1. Thereafter, hematology samples

may be obtained anytime within the 24 hours prior to the carfilzomib administration, and full or abbreviated chemistry panels may be performed up to 72 hours prior to carfilzomib administration.

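### The window, evaluability and blood-count rules do not fit the two duration-based hematologic DLTs, so the 2-in-8 gate can undercount prolonged cytopenias

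*Protocol*

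**What the plan says.** - **DLT window (Protocol 5.2).** Toxicity "will be evaluated during Cycle 1 (Cohorts 1, 2, and 3), or Cycles 1 and 2 (Cohort 4"). A subject who does not finish this period for reasons unrelated to toxicity is unevaluable and may be replaced.
- **Duration criteria (Protocol 5.2.2).** Grade 4 neutropenia (ANC below 500/mm³) "lasting for > 7 days"; Grade 4 thrombocytopenia (platelets below 25,000/mm³) "that persists for > 14 days with or without platelet transfusion, despite holding treatment".
- **Scheduled counts (Protocol 10.1.6).** Hematology "will be performed at Screening, on Days 1, 8, and 15 of each cycle, and at EOT". After screening, samples "may be obtained anytime within the 24 hours prior to the carfilzomib administration".
- **Follow-up counts (Protocol 9.2.2.1, recommended actions).** Once platelets fall below 30 × 10⁹/L, Table 7 says "Hold dose, follow CBC weekly". Once ANC falls below 0.75 × 10⁹/L, Table 8 says "Follow CBC weekly". Carfilzomib is held for platelets below 30 or ANC below 0.5 × 10⁹/L.
- **Evaluability (Protocol 5.4).** A subject is evaluable after receiving every planned carfilzomib dose (with minimum shares of the other two drugs), or after at least one carfilzomib dose and a DLT before study treatment for Cycle 1 (Cycle 2 in Cohort 4) is complete. Subjects who are not evaluable may be replaced.
- **Gate (Protocol 5).** Expansion requires "not more than 2 dose-limiting toxicities in 8 DLT-evaluable subjects at the dose selected for Dose-expansion".
- **SAP.** Section 2.2 promises the number and percentage of subjects with DLTs at each dose level, and Section 9.6.1 a DLT listing. Section 6 defines no DLT-evaluable set.

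**The concern.** A criterion that needs more than 14 days of persistence takes up over half of a 28-day window. Between Day 15 and the next cycle's Day 1 there is no scheduled count for 14 days. The protocol says neither how duration is derived from spaced counts nor what happens to an episode that starts inside the window and reaches its duration after it.

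Section 5.4 adds a second route of loss. Low counts lead to held carfilzomib, and a missed dose breaks the all-doses condition. The subject then stays evaluable only if the DLT is complete before treatment for the cycle ends. A subject with prolonged marrow toxicity can therefore be classed unevaluable and replaced, although Section 5.2 names only reasons unrelated to toxicity as grounds.

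At stake are the count that opens an expansion arm and the DLT percentages the SAP will report.

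**Working it through.** **1. The plan's own figure.** With a beta (0.5, 0.5) prior and 3 DLTs in 8, the posterior is beta (3.5, 5.5). P(rate > 0.33) = 0.621, against 0.62 in Protocol 13.7 and SAP 3.2. The interval 0.12 to 0.71 also reproduces. The DLT arithmetic is sound; the question is what enters the count.

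**2. Single-cycle window (Cohorts 1 to 3).** Assumptions: nominal days; the cytopenia stays low once it starts; onset on Days 2 to 28 (27 days); duration = last low count minus first low count. Counts: Days 8 and 15; Day 22 if a low value was seen by Day 15; Day 29 (Cycle 2 Day 1, pre-dose).

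| Onset | First low | Span to Day 22 | Span to Day 29 | ANC > 7 days? | Platelets > 14 days? |
|---|---|---|---|---|---|
| Days 2–8 | Day 8 | 14 | 21 | yes, by Day 22 | only with Day 29 |
| Days 9–15 | Day 15 | 7 | 14 | only with Day 29 | no |
| Days 16–28 | Day 29 | – | 0 | no | no |

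- Platelets: 0 of 27 onset days through Day 22; 7 of 27 with Day 29.
- Neutrophils: 7 of 27 through Day 22; 14 of 27 with Day 29.

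**3. How much is window length.** With daily counts through Day 28, platelets could be shown low for more than 14 days only for onset by Day 13 (28 − 13 = 15), or 12 of 27 days. The window alone removes 15 of the 27.

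**4. Cohort 4.** The window is 56 days. Onset on Days 16 to 28 is first seen on Day 29 and can be followed weekly to Day 50 (50 − 29 = 21). Over onset Days 2 to 56 (55 days), platelets can be shown for 28 days through Day 50 and 35 with Day 57. Every Cycle 1 onset is covered. The gap returns in Cycle 2, this cohort's only window cycle at 70 mg/m²: a count first low on Day 43 spans 57 − 43 = 14.

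**5. Evaluability.** Cycle 1 treatment ends with dexamethasone on Day 22.
- Platelets first low on Day 8 exceed 14 days on Day 23.
- ANC first low on Day 15 exceeds 7 days on Day 23.

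Both fall one day after treatment ends. If the carfilzomib held on Day 8 or 15 is not given, the subject fails both conditions of Section 5.4. If completion of treatment is instead read as Day 28, no scheduled or weekly nominal count lies between Day 22 and Day 29 to show the duration. A fall first seen on Day 29 works differently: the carfilzomib doses were all given, so on that condition the subject can stay in the denominator with no DLT.

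**6. Illustration at the gate.** The documents give no rate of prolonged cytopenia, so let f be an assumed share of true DLTs that is lost. With a true rate of 0.33, the chance of passing is P(X ≤ 2 | n = 8).
- Lost subjects counted as non-DLT: rate = 0.33(1 − f).
- Lost subjects replaced: rate = 0.33(1 − f)/(1 − 0.33f).

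| f | Rate, non-DLT | P(pass) | Rate, replaced | P(pass) |
|---|---|---|---|---|
| 0 | 0.330 | 0.476 | 0.330 | 0.476 |
| 0.10 | 0.297 | 0.559 | 0.307 | 0.534 |
| 0.25 | 0.2475 | 0.685 | 0.270 | 0.629 |

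**The case against.** A reader might infer that late marrow toxicity cannot enter the count and that the gate is biased toward acceptance. The documents do not support that, for these reasons, all of which stand:

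- **Silence is not exclusion.** No passage says that a window-crossing episode is left out. Excluding it is one reading.
- **The dating rule is an assumption.** Protocol 12.2.1.1 collects onset and resolution dates. Dated that way, ANC low on Days 15 and 22 and recovered on Day 29 lasts 14 days and qualifies. On scheduled counts alone that convention can even overcount: a 2-, 4- or 6-day neutropenia is recorded as longer than 7 days for 7%, 14% or 21% of onset days (2/28, 4/28, 6/28). With the weekly counts this falls to 0%.
- **Detection is not the platelet problem.** No gap exceeds 14 days, so every thrombocytopenia longer than 14 days is low at some scheduled count. Both weekly-count triggers lie above the Grade 4 limits, except for an optional platelet threshold of 20 for subjects with marrow involvement above 50%.
- **Nominal days matter.** Dosing windows of ±2 days can move a 14-day span either way.
- **The gate is not mechanical.** The Cohort Safety Review Committee sees all safety data and changed the NDMM regimen after two SAEs. Febrile neutropenia, and Grade 3 or 4 thrombocytopenia with bleeding above Grade 1, count as DLTs with no duration requirement.
- **Little is left to decide.** SAP Table 1 shows all six groups enrolled, so no expansion decision remains.

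These points limit the claim. They do not supply the missing rule, and they do not reconcile Section 5.4 with Section 5.2. Broader committee review does not replace a DLT count that Section 5 makes a condition. The SAP change log also says that DLTs were found to have been evaluated in cycles other than those the protocol names, so the boundary mattered in practice.

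**Conclusion.** The concern holds in limited form. The rules on window, evaluability and counts leave the status of a prolonged Grade 4 cytopenia undefined when it starts after about Day 8 (platelets) or Day 15 (neutrophils) of a single-cycle window, or correspondingly late in Cycle 2 of Cohort 4. Read literally, Section 5.4 also lets some of these subjects drop out of the denominator. The 2-in-8 gate and the SAP's DLT percentages can therefore undercount. That they did is not shown.

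The onset-day shares rest on nominal visits, sustained cytopenia and low-to-low dating, and much of the platelet effect comes from window length rather than the count schedule. The gate probabilities rest on an assumed f and illustrate sensitivity only. Severity is moderate: what remains is correct classification and reporting for Cohorts 1, 2 and 4.

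**What to change.** Leave grades, durations and doses unchanged, and reconcile Protocol 5.2, 5.4, 9.2.2.1 and 10.1.6.

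1. Attribute a Grade 4 cytopenia to the DLT window by its onset date.
2. Determine its duration from the next-cycle Day 1 count and the weekly counts already recommended in Tables 7 and 8.
3. State the dating convention: low-to-low or onset-to-recovery, how spans of exactly 7 or 14 days are treated, and to which cycle a value first low at the pre-dose Day 1 count belongs.
4. Keep the subject's DLT and evaluability status open until the duration is resolved, and make Sections 5.2 and 5.4 agree on whether a subject whose dose was held for toxicity can be replaced.
5. Use the same classification for the SAP's DLT summary and listing, state the denominator, and re-check Cohorts 1, 2 and 4.

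**Cost.** Protocol and SAP wording plus one re-check of existing data. Where a review is still pending, the committee may wait up to about 2 weeks for an unresolved case. Strict low-to-low dating of platelets first low on Day 29 would need the Day 50 count, about 3 weeks, because Day 43 gives exactly 14 days.

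**What remains.** A neutropenia that starts after Day 15 and recovers before Day 29 is still unseen: for 8, 10 or 12 days' duration, (14 − d)/28 = 21%, 14% or 7% of onset days. That should be stated as a limitation; no extra blood draw is proposed.

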5.3 COHORT SAFETY REVIEW COMMITTEE

A CSRC comprised of the lead investigator, selected additional investigators, the sponsor study medical monitor, and sponsor's drug safety representative will review all available safety data and make recommendations regarding ongoing enrollment and opening of subsequent cohorts during the Dose-evaluation Components. The CSRC will also select the KRd regimens to be evaluated in the Dose-expansion Components.

5.4 PART 1: DOSE-EVALUATION COMPONENT

Approximately 8 dose-evaluable subjects will be enrolled into each Dose-evaluation cohort ([Table 2](#), [Figure 1](#)). Enrollment will be gated such that the first 4 subjects in Cohort 1 will complete Cycle 1 and undergo a safety evaluation prior to further enrollment.

- If ≥ 2 of the first 4 subjects of Cohort 1 experience a DLT, enrollment to that cohort will stop and the study will terminate
- If ≤ 1 of the first 4 subjects experience a DLT, the cohort will recommence enrollment of an additional 4 subjects for up to 8 dose-evaluable subjects total
 - Cohort 2 (n = approximately 8) will open to enrollment

When both Cohorts 1 and 2 are open for concurrent enrollment, subjects will be assigned to a cohort on an alternating basis. Safety will be evaluated in both cohorts on an ongoing basis.

- If ≥ 2 of the first 4 subjects experience DLTs or ≥ 3 subjects experience DLTs at any time in Cohort 2, enrollment to that cohort will be stopped, and the optional third cohort (Cohort 3) may be opened to enrollment of an additional 8 subjects (approximately).
- The CSRC will review all evaluable safety data ([Section 5.3](#)). If < 3 subjects experience a DLT in an opened cohort, that dose may be selected for dose expansion.
- For NDMM subjects evaluated in Cohort 4, the CSRC will review all safety data from the first 2 cycles and may elect to expand NDMM enrollment

To be DLT evaluable, subjects must have received all planned doses of carfilzomib, at least 80% of planned doses of lenalidomide, and at least 75% of planned doses of dexamethasone or received at least 1 dose of carfilzomib and experienced a DLT prior to completion of study treatment for Cycle 1 (Cohorts 1-3) or Cycle 2 (Cohort 4). Subjects who withdraw from treatment after receiving a dose of carfilzomib but before completing the first 28-day cycle (Cohorts 1-3) or the first two 28-day cycles (Cohort 4) for reasons unrelated to toxicity will be considered unevaluable for DLTs. Subjects who are not DLT-evaluable may be replaced.

The schema for the Dose-evaluation Component of the study for RRMM subjects is presented in [Figure 2 \(Appendix E\)](#).

Cohort 4

A 2-step-up KRD regimen will be evaluated in NDMM subjects: carfilzomib will be given at 20 mg/m² on Day 1 of Cycle 1, 56 mg/m² on Days 8 and 15 of Cycle 1, then at 70 mg/m² on Days 1, 8, and 15 beginning with Cycle 2 (Cohort 4; [Table 2](#)). This regimen was selected by the CSRC for dose-evaluation in NDMM subjects, after the occurrence of 2 SAEs in NDMM subjects during Cycle 1 of treatment at Cohort 2 dose level during the **Arm 1** NDMM Dose-expansion ([Figure 1](#)).

5.5 PART 2: DOSE-EXPANSION COMPONENT

Per protocol amendment 2:

Enrollment of NDMM into Dose-expansion Arm 1 will stop ([Appendix E; Figure 3](#)).

NDMM subjects will be enrolled into Dose-evaluation Cohort 4 ([Figure 1; Table 2](#)). Arm 1 subjects enrolled prior to protocol amendment 2 who are DLT evaluable at Cohort 4 dosing will be included in Dose-evaluation Cohort 4 ([Figure 1; Table 2](#)).

The CSRC will evaluate all safety data for all NDMM subjects. Following the **DLT** rules above, the CSRC may elect to open an NDMM Dose-expansion **arm**, and may enroll an additional 30 NDMM subjects ([Section 5.4](#)).

5.6 ACTIVE FOLLOW-UP

Subjects who have terminated or completed study treatment (for reasons other than progressive disease, allogeneic stem cell transplant, death, or withdrawal of consent) will enter Active Follow-up for 1 year. For subjects in Active Follow-up, tumor response and disease assessment measurements will be performed every 8 weeks (every 56 ± 4 days). The investigators will make every reasonable effort to keep each patient in active follow-up for 1 year, or until the subject has progressive disease (PD), begins treatment with any antimyeloma medication, has withdrawn consent for further participation, is lost to follow up, has died, or the study is closed, whichever is earliest.

5.7 ESTIMATED STUDY DURATION AND STUDY CLOSURE

The total study duration is expected to be a minimum of 60 months. Approximately 6 months will be required to enroll subjects in the RRMM Dose-evaluation Component of the study. Approximately 9 months will be required to enroll subjects in the RRMM Dose-expansion Component of the study. Subjects will be followed for up to 17 months in order to complete primary safety and efficacy evaluations with up to an additional 12 months of Active Follow-up.

It will take up to approximately **12** months to enroll NDMM subjects into Dose-evaluation Cohort 4, review the safety data, and enroll NDMM subjects into the NDMM Dose-expansion **Arm 3**. Subjects will be followed for up to 17 months on treatment (with an allowed interruption of up to 4.5 months for ASCT), and for 12 months for Active Follow up.

Based on these assumptions, it is estimated that the final analysis will occur approximately 60 months after the first subject is enrolled.

The end of study will occur when the last subject leaves Active Follow-up.

5.8 MINIMIZING BIAS

5.8.1 *RANDOMIZATION*

This is not a randomized study.

Subjects in the RRMM Dose-evaluation Component will be assigned to the open cohort at time of enrollment; when/if Cohort 1 and Cohort 2 are both open to enrollment, enrollment will alternate between Cohort 1 and Cohort 2 until Cohort 1 is filled.

5.8.2 *BLINDING*

This is an open-label study; there is no blinding.

